1.0 SCHEMA

- Title:** Swaziland HIV Incidence Measurement Survey (SHIMS)
- Short Title:** HIV Incidence in Swaziland
- Protocol Co-Chairs:** [name], [name], [name], and [name]
- Background:** The Government of the Kingdom of Swaziland plans to scale-up HIV prevention, care and treatment public health programs over a twelve-month period, including the Male Circumcision Accelerated Saturation Initiative (MC ASI) campaign. The MC ASI *program* will track the number of MC procedures but will not evaluate the impact of the campaign on the HIV epidemic. This research study will neither provide nor promote male circumcision services.
- Purpose:** To determine HIV incidence at a population level before and after the independent public health program--Male Circumcision Accelerated Saturation Initiative (MC ASI)—and concurrent with the expansion of other HIV prevention, care and treatment programs in Swaziland
- Design/
Duration:** Two separate cross-sectional household surveys, one before and one after MC ASI, in order to identify three prospective, longitudinal observational cohorts
- Two independent separate short term cohorts representative samples of HIV-uninfected adult men and women before and after completion of the MC ASI. (Cohort “A1” before ASI, and “A2” after ASI). Cohort A1 is followed for 6 months; Cohort A2 is followed for 12 months.
- One long-term cohort (Cohort “B”) comprised of a subset of the highest risk age groups of men and women from Cohort A2. Cohort B is followed for an additional 6-18 months (beyond the 12 months of Cohort A2).
- One cross-sectional observational survey (Cross-Sectional Cohort “C”) comprised of a subset of HIV-infected men and women who participated in Pre-Cohort A1. Cohort C participants are visited approximately 6 to 12 months after the initial A1 visit.
- Sample Size:** A total of approximately 34,421 individuals from a sample of approximately 30,645 households over a 3 1/2-year period will be included in the study. Of the 34,421, a subset of 26,618 individuals

will participate in either Cohort A1, Cohort A2, or in A2 and B, as follows:

- 1) Two cross-sectional household surveys: 14,884 households for A1 and 15,758 households for A2.
- 2) Two separate, nationally representative, HIV-uninfected longitudinal cohorts of 5,823 men and 7,106 women (Cohort A1) and 6,165 men and 7,524 women (Cohort A2)
- 3) One longitudinal sub-cohort consisting of a subset of HIV-uninfected individuals from Cohort A2, with 1,541 men ages 25-34 and 2,182 women ages 18-24 (Cohort B)
- 4) One cross-sectional survey (Cohort C) comprised of a subset of 1,000 HIV-infected men and women ages 18-49 who participated in the Pre-Cohort A1

Study Objectives:

Primary Objectives

- 1a) To estimate HIV incidence rates in a household-based, nationally representative sample of men ages 18-49 before and after completion of the MC ASI.
- 1b) To estimate HIV incidence rates in a household-based, nationally representative sample of women ages 18-49 before and after completion of the MC ASI.
- 2a) To estimate HIV incidence rates in a highest risk age subset of the household-based, nationally representative sample, men ages 25-34, for an additional 6-18 months after the MC ASI completion.
- 2b) To estimate HIV incidence rates in a highest risk age subset of the household-based, nationally representative sample, women ages 18-24, for an additional 6-18 months after the MC ASI completion.
- 3) To estimate HIV incidence rates of circumcised men as compared to uncircumcised men in a household-based, nationally representative sample of men after completion of the MC ASI.

Secondary Objectives

- 1) To examine the association of baseline demographic characteristics and HIV incidence and prevalence in a household-based representative sample of men and women before and after completion of the MC ASI.
- 2) To determine the prevalence of circumcision among a

household-based representative sample of men before and after completion of the MC ASI.

- 3) To estimate HIV prevalence rates among men and women in a household-based representative sample of men and women before and after completion of the MC ASI.
- 4a) To describe sexual risk behavior and exposure to sexual risk reduction campaigns in a household-based representative sample of men and women before and after completion of the MC ASI.
- 4b) To assess sexual risk behaviors in a highest risk age subset of the household-based, nationally representative sample, men ages 25-34, for an additional 6-18 months after the MC ASI completion.
- 4c) To assess sexual risk behaviors in a highest risk age subset of the household-based, nationally representative sample, women ages 18-24, for an additional 6-18 months after the MC ASI completion.
- 5) To describe the proportion of HIV-infected men and women in a household-based representative sample with undetectable viral loads before and after completion of the MC ASI.
- 6) To measure the proportion of HIV-infected men and women in a household-based representative sample who report engagement in HIV care and ART use before and after completion of the MC ASI.
- 7) To estimate the annual number of HIV infections averted among men due to MC.
- 8) To describe the concurrent CD4 count and viral load distributions in a household-based, nationally representative sample of HIV-infected men and women ages 18-49, within the context of ART use.
- 9) To estimate the proportion of HIV-infected men and women ages 18-49 who have a CD4 count <350 cells/ mm^3 and who report no current ART use.

Study**Outcomes:**Primary outcomes

- HIV incidence rates in men and women
- HIV incidence in circumcised and uncircumcised men

Secondary outcomes

- HIV prevalence rates in men and women
- Sexual risk behaviors
- Viral load in HIV-infected men and women
- Rates of engagement in HIV care
- Rates of ART use
- Prevalence of circumcision in men
- Exposure to other HIV prevention intervention
- CD4 count in HIV-infected men and women
- Proportion of HIV-infected men and women who report no current ART use

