2.0 INTRODUCTION

2.1 Literature Review/Background

The HIV/AIDS epidemic in sub-Saharan Africa and Swaziland

Approximately 33.2 million (30.6-36.1 million) adults and children were living with HIV worldwide in 2007, and an additional estimated 2.5 million (1.8-4.1 million) new HIV infections occurred that year alone [UNAIDS, 2010]. Young adults (ages 15-24) have the highest HIV incidence and account for 45% of all new HIV infections. Sub-Saharan Africa continues to be the most heavily affected region accounting for approximately 68% and 90% of the world's adult and childhood HIV prevalent cases, respectively [UNAIDS, 2010]. Despite HIV prevention efforts, incidence rates in the region remain high with an estimated 1.9 million (1.6-2.1 million) adults and children newly infected with HIV in 2007. These high incidence rates, combined with increased survival rates due to expanded HIV care and treatment programs, contribute to the high HIV prevalence rates observed in the region.

Swaziland, a small landlocked country in southern Africa, has the highest HIV prevalence in the world. With approximately 1.1 million people, HIV prevalence is estimated at 26% for men and women ages 15-49 years with only modest differences in urban (31%) and rural (24%) regions [UNAIDS, 2010]. HIV prevalence differs significantly by sex with rates higher in women than men (31% v 20%). In addition, for women, prevalence peaks at age 25-29 (49%), while prevalence peaks at age 35-39 (45%) for men. HIV incidence rates are also high among both men and women. Among females 15-24 and males 25-34 years the annual HIV incidence is estimated to be 6% and 5%, respectively. The primary driver of the HIV epidemic in Swaziland, as in the rest of sub-Saharan Africa, is heterosexual sex [UNAIDS, 2010].

The Government of the Kingdom of Swaziland (GKOS) has provided antiretroviral therapy (ART) to persons with advanced HIV infection since 2003. In line with international guidance, the GKOS 2006 national treatment guidelines recommended ART for adults with a CD4 count below 200 cells/mm³ [Ministry of Health, 2006]. National guidelines were recently revised to reflect 2010 WHO guidance, and recommend ART at a CD4 threshold of 350 cells/mm³ [Ministry of Health, 2010].

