4.2 How study design meets objectives and addresses research questions

The study design incorporates two different strategies for measuring the change in seroincidence. To measure the population effect of the MC ASI campaign on HIV infection in Swaziland, we plan two independent household based samples, one prior to the campaign, one 12 months after the completion of the campaign. Each gives an

independent population “snapshot” of the current rates of infection. The second strategy enrolls a cohort of men and women in the ages at highest risk prior to the MC ASI and measures that seroincidence in this group for an additional 6-18 months after the campaign’s completion. There are several reasons for this hybrid approach. Two sequential short term cohorts provide two similar ‘snapshots’ of HIV incidence before and after the ASI campaign and coinciding with scale-up of other prevention programs. These two cohorts are representative of the national population and the HIV seroincidence estimates before and after ASI are therefore likely to represent actual changes in the epidemic. The use of a more traditional longitudinal cohort is conceptually familiar from randomized placebo controlled clinical trials; here it is used to follow HIV incidence among young adults in the highest incidence age groups over an additional 6-18 month period.

The comparison of HIV incidence rates between circumcised and uncircumcised men offers insight into the role played by MC in reducing HIV infection in the cohort and in the general population, if observed.

Blood specimens from persons identified as HIV-infected *during pre-cohort surveys* (A1 and A2) will be collected to measure viral load. These data will be used to determine the proportion of HIV infected persons with undetectable viral load in the community. The proportion of undetectable viral load at the baseline pre-cohort survey will be compared to the post-MC ASI pre-cohort survey to explore the potential effect of scale up of the ART program and viral suppression on reduced HIV incidence in the general population, if observed.

Blood specimens to measure CD4 count will be collected using a multistage clustered random sample of persons who were identified as HIV-seropositive at the pre-cohort survey for Cohort A1 (T1). These data will be used to estimate the CD4 count distribution, viral load distribution, and self-reported ART use among HIV-infected individuals at the population-level.

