4.4 Limitations to the study designs

The accelerated nature of the MC ASI prevents the use of evaluation designs that allow causal inference to a particular intervention such as serial rollout of different interventions or of establishment of one intervention in certain geographic areas and not others. In addition, given the overwhelming evidence of the efficacy of MC at preventing HIV acquisition among men, it would be unethical to have a true comparison group, even if that group were wait-listed for services. Instead, multiple evaluation designs and data collection on other factors that could influence HIV incidence besides an increase in MC prevalence will be used in an attempt to distinguish the effect of each of these variables on HIV incidence. For example, data on HIV-related sexual risk behaviors will be collected to determine if changes HIV incidence coincide with change in risk behaviors, resulting from the MC ASI or other ongoing HIV prevention interventions. Additionally, data on prevalence of persons on ART and proportion of persons with undetectable viral load will be collected to assist in understanding the potential effect of expanding care and treatment services on changes in HIV incidence. Cohort effects are a major threat to validity due to power reductions or bias from loss to follow-up and repeated measures (i.e. repeated counseling and interview sessions with staff reduces HIV acquisition risk among cohort participants over time). The two short term cohorts, with their one-time 6 or 12 month follow up will minimize cohort effects. The hybrid approach with addition of a longer term cohort with multiple follow-up observations will allow comparison of measurements from the different methodologies.

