8.1.4 Analysis of secondary objectives

- 1) To examine the association of baseline demographic characteristics with HIV incidence and prevalence in a household-based representative sample of men and women before and after completion of the MC ASI. Within each cohort, logistic regression will be used to assess association of baseline demographic characteristics with HIV prevalence. Poisson, survival and logistic regression will be used as appropriate to assess associations with seroincidence and baseline demographics. Combined analysis of predictors of seroprevalence and seroincidence using both cohorts will assess effect modifiers associated with cohort (e.g. time) using test for interaction with time. Sample weights will be used in all analyses.
- 2) To determine the prevalence of circumcision among men before and after completion of MC ASI. Population-based circumcision prevalence rates will be computed using appropriate sample weights.
- 3) To estimate HIV prevalence rates among men and women before and after completion of the national male circumcision ASI. Population-based age and gender HIV prevalence rates will be computed using appropriate sample weights.
- 4) To describe sexual risk behavior in a household-based representative sample of men and women before and after completion of the MC ASI. This analysis will be conducted in both HIV-infected and HIV-uninfected participants. Sexual risk behaviors compared between the enrollment pre and post- MC ASI surveys will include the proportion of men and women reporting any unprotected sex and proportion reporting more than one partner. Logistic regression will be used to assess differences in proportions between the baseline cohorts, adjusted for baseline demographic factors, HIV status, and circumcision status (men).

In the two longer longitudinal cohorts of younger HIV-uninfected men (25-34 yrs) and women (18-24 yrs), logistic regression will be used to compare change in behavior from baseline to follow-up. Factors predicting increase and decrease in risk behaviors will be assessed.

- 5) To describe the proportion of HIV-infected men and women in a household-based representative sample of men with undetectable viral loads before and after completion of MC ASI. Logistic regression will be used to assess differences in proportions of male participants with undetectable viral load.

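### Suppression among HIV-infected people does not by itself show whether exposure to viraemic partners changed, and its planned pre/post test covers men only

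*Protocol*

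**What the plan says.** Secondary Objective 5 (Protocol 1.0 and 3.2), where completion refers to the MC ASI, is "To describe the proportion of HIV-infected men and women in a household-based representative sample with undetectable viral loads before and after completion". Section 4.2 uses the same denominator: viral load data will "determine the proportion of HIV infected persons with undetectable viral load in the community". It then gives the pre/post comparison a purpose, "to explore the potential effect of scale up of the ART program and viral suppression on reduced HIV incidence in the general population, if observed". Section 4.4 says of the prevalence of ART use and the proportion undetectable that these data "will be collected to assist in understanding the potential effect of expanding care and treatment services on changes in HIV incidence".

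The analysis in 8.1.4 item 5 is: "Logistic regression will be used to assess differences in proportions of male participants with undetectable viral load". HIV prevalence is a separate objective (Secondary Objective 3), estimated with weights from the same two surveys. ART use and engagement in care (Secondary Objective 6) also have HIV-infected people as the denominator. No section combines prevalence with suppression.

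**The concern.** The proportion undetectable among the infected suits its role as an ART-programme indicator. Sections 4.2 and 4.4 ask something else of it: help in explaining a change in incidence among the uninfected. What an uninfected adult meets is the share of potential partners who are infected and have detectable virus. That share depends on prevalence as well as suppression, and ART can move both. Section 2.1 says of sub-Saharan Africa that high incidence, combined with "increased survival rates due to expanded HIV care and treatment programs, contribute to the high HIV prevalence rates observed in the region". Suppression among the infected can therefore improve while the viraemic share of adults stays level.

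The second problem is an inconsistency. The objective covers men and women, but the stated test covers men. Section 2.1 names heterosexual sex as the main driver of the epidemic, so men's viraemia bears chiefly on women's incidence. Women's viraemia bears chiefly on men's incidence, and men's incidence is what the study is powered for. The stated test leaves women out.

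At stake is how an observed fall in incidence is interpreted when several programmes expand together, a difficulty the protocol acknowledges in 2.3 and 4.4.

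**Working it through.** **No plan figure to reproduce.** Section 7.2 limits power considerations to the primary objectives, apart from the precision calculations for Cohort C. The baseline proportion undetectable in the two surveys is not given, so all values of s below are assumptions.

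**Identity.** Let P be HIV prevalence, s the proportion undetectable among the infected, and V the share of all adults who are infected with detectable virus. Then V = P × (1 − s). V is unchanged when P2 = P1 × (1 − s1)/(1 − s2).

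**Inputs from the protocol.** Section 2.1: "HIV prevalence is estimated at 26% for men and women ages 15-49 years". Sample-size factors in 7.2: 77% of men and 65% of women uninfected, so P = 23% and 35%; 99% agree to cohort enrolment; design effect 1.25. Section 7.2 allows a design effect of up to 3 for Cohort C, used here as a pessimistic bound.

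**Rise in prevalence that exactly offsets a rise in suppression.**

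| P1 | s1 to s2 (assumed) | V | P2 needed |
|---|---|---|---|
| 26% | 30% to 35% | 18.2% | 28.0% |
| 26% | 30% to 40% | 18.2% | 30.3% |
| 26% | 40% to 50% | 15.6% | 31.2% |
| 23% (men) | 30% to 35% | 16.1% | 24.8% |
| 35% (women) | 30% to 35% | 24.5% | 37.7% |

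First row: 0.26 × 0.70 = 0.182 and 0.28 × 0.65 = 0.182.

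**Could prevalence move that far?** The protocol's incidence figures are 2.0 (men) and 3.0 (women) per 100 person-years. The surveys are about 24 months apart as stated in 4.0, or 30 months from the enrolment points at month −6 and month 24. New infections would add at most 0.74 × (1 − 0.98²) = 2.9 points to 0.74 × (1 − 0.97^2.5) = 5.4 points, before deaths and ageing out. Starting from P = 26% and s = 30%, that could fully offset a rise in s to between 1 − 0.182/0.289 = 37% and 1 − 0.182/0.314 = 42%.

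**Would the suppression comparison still show a difference?** Expected HIV-infected survey participants, from planned enrolment:
- A1: 5,823/(0.99 × 0.77) × 0.23 + 7,106/(0.99 × 0.65) × 0.35 = 1,757 + 3,865 = 5,622.
- A2: 6,165/(0.99 × 0.77) × 0.23 + 7,524/(0.99 × 0.65) × 0.35 = 1,860 + 4,092 = 5,952.

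For 30% versus 35%, SE = √[D × (0.30 × 0.70/n1 + 0.35 × 0.65/n2)]:

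| Group | D = 1.25 | D = 3 |
|---|---|---|
| Both sexes | SE 0.0097, z = 5.1 | SE 0.0151, z = 3.3 |
| Men only | SE 0.0174, z = 2.9 | SE 0.0269, z = 1.9 |

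Building the counts from participating households instead gives about 6,091 and 6,448. The difference lies in the men: the listed male factors give 1/(0.92 × 0.77 × 0.99 × 0.90 × 0.95) = 1.67, not the printed 2.11. With those larger counts, power for 30% versus 35% is above 99% (D = 1.25) or 93% (D = 3) for both sexes, and 90% or 55% for men alone. The choice of count does not change the conclusion.

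**What an unchanged V does not show.** With prevalence at 28% and suppression still at 30%, V would be 0.28 × 0.70 = 19.6% rather than 18.2%. A level V is therefore compatible with ART having lowered exposure relative to no improvement in suppression.

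**The case against.** The plan contains no rule that turns a rise in suppression into an ART effect. The objective is to describe, 4.2 is to explore, and 4.4 treats these data as an aid to understanding. Suppression is one indicator among several, beside ART use, risk behaviour and programme data. Prevalence is reported from the same surveys, so a reader could multiply the two figures. Sections 2.3 and 7.1 rule out attributing a change to the MC ASI alone. The circumcision contrast (Primary Objective 3) does not depend on viral load.

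All of this stands, and it limits the point. A reader might infer that the plan would wrongly credit ART for a fall in incidence, or would miss a fall in viraemia driven by prevalence. The documents support neither: no attribution rule is stated, and Objective 3 would show the change in prevalence. Section 2.1 describes regional prevalence and does not forecast a rise in Swaziland between the surveys. The offsetting values above are chosen to cancel. A significant rise in suppression in the example would be a true finding about suppression.

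Nor is V a cleaner attribution measure. It also moves with new infections, deaths and ageing, so it should not replace the conditional proportion.

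Two things remain. The caveats about sole attribution to the MC ASI do not say whether the ART indicator tracks exposure. And the men-only wording conflicts with the objective whatever one makes of the denominator.

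**Conclusion.** The point holds as a limit on an exploratory comparison. The proportion undetectable among the infected cannot show alone whether exposure of uninfected adults changed; that follows from the identity for any values. The example (26% to 28%, 30% to 35%, V constant at 18.2%) rests on assumed suppression levels and an assumed rise in prevalence. Full offset is plausible only for modest gains in suppression, up to roughly 7 to 12 points from a 30% baseline, and that range is an upper bound because deaths and ageing out are ignored. A larger gain would usually lower V as well.

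The mismatch between an objective for both sexes and a test for men rests on no assumption. Overall this is a free improvement.

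**What to change.** In 8.1.4 item 5:

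1. State the pre/post test of the proportion undetectable for women as well as men.
2. Keep that proportion as the ART-programme indicator.
3. Add the weighted prevalence of viraemia among all tested adults 18–49 (HIV-positive with detectable viral load, divided by all tested), by sex, pre versus post, with confidence intervals.
4. Present it together with HIV prevalence and the conditional proportion. Set women's viraemia beside men's incidence, and men's beside women's.
5. State that a change, or no change, in viraemia prevalence also reflects new infections, deaths and ageing, and does not alone establish or exclude an ART effect.

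This needs no new data. Section 6.1.2 reclassifies those who decline the rapid test as refusing the study, so survey participants are tested, and 6.5.1 and 6.7.2 plan viral load for those who test positive. The cost is one more weighted proportion per sex and survey.

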2.0 INTRODUCTION

2.1 Literature Review/Background

The HIV/AIDS epidemic in sub-Saharan Africa and Swaziland

Approximately 33.2 million (30.6-36.1 million) adults and children were living with HIV worldwide in 2007, and an additional estimated 2.5 million (1.8-4.1 million) new HIV infections occurred that year alone [UNAIDS, 2010]. Young adults (ages 15-24) have the highest HIV incidence and account for 45% of all new HIV infections. Sub-Saharan Africa continues to be the most heavily affected region accounting for approximately 68% and 90% of the world's adult and childhood HIV prevalent cases, respectively [UNAIDS, 2010]. Despite HIV prevention efforts, incidence rates in the region remain high with an estimated 1.9 million (1.6-2.1 million) adults and children newly infected with HIV in 2007. These high incidence rates, combined with increased survival rates due to expanded HIV care and treatment programs, contribute to the high HIV prevalence rates observed in the region.

Swaziland, a small landlocked country in southern Africa, has the highest HIV prevalence in the world. With approximately 1.1 million people, HIV prevalence is estimated at 26% for men and women ages 15-49 years with only modest differences in urban (31%) and rural (24%) regions [UNAIDS, 2010]. HIV prevalence differs significantly by sex with rates higher in women than men (31% v 20%). In addition, for women, prevalence peaks at age 25-29 (49%), while prevalence peaks at age 35-39 (45%) for men. HIV incidence rates are also high among both men and women. Among females 15-24 and males 25-34 years the annual HIV incidence is estimated to be 6% and 5%, respectively. The primary driver of the HIV epidemic in Swaziland, as in the rest of sub-Saharan Africa, is heterosexual sex [UNAIDS, 2010].

The Government of the Kingdom of Swaziland (GKOS) has provided antiretroviral therapy (ART) to persons with advanced HIV infection since 2003. In line with international guidance, the GKOS 2006 national treatment guidelines recommended ART for adults with a CD4 count below 200 cells/mm³ [Ministry of Health, 2006]. National guidelines were recently revised to reflect 2010 WHO guidance, and recommend ART at a CD4 threshold of 350 cells/mm³ [Ministry of Health, 2010].

HIV testing coverage is relatively low, with 17% and 36% of men and women 15-49 years reporting having ever been tested and receiving test results [CSO, 2008.] In contrast, projections of ART coverage, based upon modeling of national health systems data, indicate widespread coverage. In 2009, approximately 45,748 HIV-infected adults were estimated to be on ART, accounting for 93% of the population projected to have a CD4 count less than 200 and 59% of the population modeled to have a CD4 count less than 350 [UNAIDS, 2010]. A more recent estimate from the 2011 MOH Quarterly Service Coverage Report places ART coverage using a CD4 threshold of 350 at 79.5% (MOH QSCR, 2011). National goals aim for 85% coverage of all ART-eligible adults (i.e. CD4 count below 350) by 2014 [NERCHA, 2009].

HIV prevention efforts in Swaziland have primarily focused on behavioral change strategies such as delaying sexual debut, encouraging partner reduction and/or fidelity to one partner, and consistent and correct condom use at every sexual encounter. Unfortunately, the success in reducing HIV incidence from these initiatives has fallen far short of the goals established by the Swazi government and the President's Emergency Plan for AIDS Relief (PEPFAR) strategies.

Lack of male circumcision (MC) has been identified as one of the key drivers of the Swazi HIV epidemic [Swaziland, 2009]. Only 8% of men reported being circumcised during the 2007 Demographic and Health Survey (DHS) [CSO, 2008]. Based on strong scientific evidence that male circumcision is efficacious at reducing HIV acquisition among men, the Swazi government developed an HIV prevention strategy with a focus on the rapid scale-up of male circumcision services nationwide.

Male Circumcision for HIV prevention

For at least a decade, multiple cross-sectional, prospective and population-level ecologic studies have identified lack of MC as a risk factor for HIV infection [Siegfried et al., 2005; Weiss et al., 2000]. In 2000, a systematic review and meta-analysis of HIV in Africa, which included 19 cross-sectional studies, five case-control studies, and one partner study, noted a substantial protective effect of MC on risk for HIV acquisition for men [Weiss et al., 2000]. In population-based studies that adjusted for confounding factors, the relative risk for HIV infection was reduced by 58% in circumcised men. For men at high risk of HIV, such as those seeking treatment for sexually transmitted infections (STI), the association was stronger (adjusted relative risk 0.29, 95% confidence interval (CI) 0.20 - 0.41). A Cochrane Review from 2003 of 35 observational studies, including many of the same studies used in the 2000 meta-analysis, found inconsistent results in 14 cross-sectional and one prospective study in the general population [Siegfried et al., 2003]. However, the single cohort study included in the meta-analysis showed a significant difference in HIV acquisition rates (odds ratio 0.58, 95% CI 0.36 - 0.96 for circumcised men). As with the earlier meta-analysis, results from the subset of 19 studies among high-risk populations found a consistent, substantial protective effect.

Three randomized controlled clinical trials (RCTs) were conducted in Africa to address the possibility that the observational findings described above were due to confounding, and to determine whether medically-performed circumcision of adult males would reduce their risk of HIV acquisition. The first study, conducted in South Africa, was stopped in 2005, and subsequent studies in Kenya and Uganda were stopped in 2006 after interim analyses from each found that medical circumcision significantly reduced male participants' risk of acquiring HIV infection [Auvert et al., 2005; Bailey et al., 2007; Gray et al., 2007]. Men who had been representatively assigned to the circumcision group had a 60% (South Africa), 53% (Kenya), and 51% (Uganda) lower incidence of HIV infection compared to men assigned to the control group to be circumcised at the end of the trials. More recent data collected through 42 months of follow-up from the Kenyan trial demonstrated an even greater protective efficacy. HIV seroincidence was 0.77/100 person years among circumcised males compared to

2.37/100 person years among control group males who did not seek circumcision after the trial ended, equating to a 68% reduction in risk of HIV acquisition [Bailey et al., 2008]. Consistent with the Kenyan data, follow-up of men in the Ugandan trial at approximately 5 years post-circumcision also revealed a 68% reduction in HIV acquisition risk among circumcised males (compared to control group males who had not undergone circumcision after the trial ended) [Kong et al., 2011].

In March 2007, WHO and UNAIDS published normative guidance on policy and program implication resulting from the weight of the evidence for MC and HIV prevention [WHO/UNAIDS, 2007]. Key conclusions and recommendations included:

- MC should now be recognized as an additional important intervention to reduce the risk of heterosexually acquired HIV infection in men;
- MC should always be considered as part of a combination HIV prevention package, which includes the provision of HIV testing and counseling services; treatment for STI; the promotion of safer sex practices, such as abstinence from penetrative sex, reduction in the number of sexual partners, and delay in the onset of sexual relations; and the provision of male and female condoms, and promotion of their correct and consistent use;
- MC should be provided with full adherence to medical ethics and human rights principles, including informed consent, confidentiality, and absence of coercion;
- Countries with high prevalence, generalized heterosexual HIV epidemics and low rates of MC should consider urgently scaling up access to MC services and that additional resources be mobilized to support this; and
- Promoting circumcision for HIV-infected men is not recommended.

The Accelerated Saturation Initiative (ASI) for Male Circumcision in Swaziland

Based upon the convincing evidence for the protective effect of male circumcision, the Government of the Kingdom of Swaziland (GKOS) convened a National MC Task Force in 2006 to guide policy and strategy development. His Majesty King Mswati III, and high level government officials including the Prime Minister, Ministerial Cabinet, and Minister of Health are all proponents of MC for HIV prevention.

Swaziland's National MC Task Force created an initial MC strategy to circumcise 80% of 15-24 year old males within 5 years, and implementation of this strategy began in 2008. In the interim, the Government of Kenya launched a national month-long MC campaign, and 36,000 boys and men were circumcised in 30 working days. Based upon Kenya's success, PEPFAR's MC Technical Working Group suggested to Swaziland that an acceleration of their strategy from 5 years to 1 year might be feasible, and PEPFAR mobilized resources to assist.

Modeling conducted by the Future's Group in support of the accelerated approach projected that circumcising 80% of 15-49 year old men in one year could avert 88,000 new HIV infections by 2025, and that 1 HIV infection could be prevented for every 3-4 circumcisions performed. Annual HIV incidence under this accelerated scenario could be reduced by approximately 70% by 2025. Consequent HIV care and treatment cost savings could total over US\$650 million over the same time period. Thus, in early 2010, the GKOS outlined an unprecedented national MC program—the MC Accelerated Saturation Initiative (ASI)—to provide voluntary medical MC to 80% of HIV-uninfected males aged 15-49 years by the end of 2011. There are approximately 240,000 15-49 year old males in the country; 92% are estimated to be uncircumcised, 80% are estimated to be HIV-negative. This equates to approximately 176,000 males that are uncircumcised and HIV-negative, 80% of which (the ASI target) equals approximately 140,000 males. Depending on the number of HIV-infected males who also seek MC after counseling regarding the lack of HIV prevention benefit, as many as 175,000 boys and men are anticipated to voluntarily receive MC services.

Program Description

The GKOS plans to launch the MC ASI in January 2011. Services delivered will include the following activities in addition to voluntary medical MC:

- information and education for both men and women on MC as an HIV prevention strategy;
- pre-operative provider-initiated HIV testing and counseling (PITC);
- individualized and partner HIV risk reduction counseling;
- syndromic screening and treatment for STIs;
- promotion and provision of male and female condoms; and
- either the offer of voluntary HIV testing and counseling (VCT) for sex partners of surgical candidates or couples HIV testing and counseling for sex partners who accompany surgical candidates to MC facilities.

For surgical candidates identified as HIV-infected during PITC, the following services will be provided, as is customary for all persons newly diagnosed with HIV in Swaziland:

- the recommendation and availability of VCT for sex partners;
- counseling regarding the lack of HIV prevention benefit from MC; and,
- referrals for HIV prevention, care, and treatment services

Efforts are underway to align MC service delivery locations with existing clinical staging and HAART-initiation centers to facilitate linkages between the MC program and HIV care and treatment program.

Approximately 35FTE service delivery teams during peak times will be required to meet the program target of reaching up to 175,000 boys and men with a comprehensive package of MC services in the 12-month period from January to December 2011. To minimize strain on existing health systems, the GKOS plans to utilize international human resources and mobile MC services to accomplish the campaign's strategic goals. It is planned that entire surgical teams—physician surgeons, nurses, surgical assistants,

cleaners, counselors—will be transported along with all necessary equipment and supplies to designated locations throughout the country. They will provide services in temporarily erected minor surgical theaters or in existing health facilities, schools or other buildings outfitted for short-term provision of MC services.

A national male circumcision performance measure—annual percentage of 15-49 year old males circumcised—is already reportable to the Swaziland National AIDS Program (SNAP), in accordance with Swaziland’s Health Sector Strategic Plan 2008-2013 (HSSP). The ASI Detailed Action Plan calls for the development of additional performance measures—Strategic Operational Objective Indicators—as ASI implementation planning progresses. PEPFAR funded partners in all countries, including Swaziland, receiving support for male circumcision must already track and report performance indicators, including the total number of males circumcised annually, and the specific number circumcised using PEPFAR funds. Disaggregations by age and HIV status are included. Existing monitoring and evaluation (M&E) activities in support of these reporting requirements will be utilized, and additional resources have been allocated (separate from this study) to reinforce the timeliness, accuracy, completeness, and uniformity of M&E activities, given the extraordinary pace and scale of the ASI campaign and the need to align reporting with the HSSP format and across multiple service providers. Though our study is independent of the ASI campaign and is thus not at all responsible for collecting ASI performance indicators, we will liaise with implementing partners and SNAP to remain apprised of progress toward the targets. Evaluation of the performance indicators will also reveal whether uptake of male circumcision services is differential by age, HIV status, and region. As appropriate, the investigators may propose modifications of the study timeline and analyses, if targets are achieved in a timeframe that varies widely from projected and/or if uptake of male circumcision is non-uniform, according to the performance indicators.

